2.1. Specific Aims

Aim 1: Determine the effectiveness of economic incentives contingent on point-of-care (POC) urine ethyl glucuronide (EtG) <300 ng/mL (Arms 2 & 4) versus no alcohol incentives (Arms 1 & 3) to reduce heavy drinking over 6 months, among HIV/TB co-infected adult drinkers receiving IPT. We will randomize participants to low-cost escalating prize incentives for EtG negative urine tests at IPT refill visits (Arms 2+4), versus no incentives (Arms 1+3).

- Hypothesis: Incentives will be more effective in promoting decreased alcohol use during IPT versus the control, resulting in less hepatotoxicity and greater IPT adherence in the intervention versus the control group.
- Outcomes: Primary: Non-heavy drinking determined by self-report (Alcohol Use Disorders Identification Test – Consumption [AUDIT-C], prior 3 months, negative) *and* phosphatidylethanol (PEth) <35 ng/mL at three *and* six months. Secondary: IPT adherence and hepatotoxicity.

Aim 2: Determine the effectiveness of economic incentives contingent on POC (IsoScreen) INH urine positive tests (Arms 3 & 4) versus no INH incentives (Arms 1 & 2) on INH adherence among HIV/TB co-infected adult drinkers. We will randomize participants to low-cost escalating prize incentives for INH positive urine tests at IPT refill visits (Arms 3+4), versus no incentives (Arms 1+2).

- Hypothesis: The incentive strategy will result in greater INH adherence versus the control.
- Outcomes: Primary: INH adherence measured as >90% pill-taking days by medication event monitoring system (MEMS) cap opening over six months. Secondary: INH concentration in hair at 3 and 6 months.

Aim 3: Assess the impact of economic incentives on HIV virologic suppression and explore their mechanisms of action, six months after trial completion. We will follow all study participants for six months after trial completion.

a) **Assess the impact of the 3 separate incentive interventions (Arms 2,3,4) vs. no incentives (Arm 1) on HIV virologic suppression.**

- Hypothesis: The intervention arms will be associated with greater viral suppression versus control.
- Outcomes: Primary: The proportion with undetectable HIV viral load six months post-IPT completion. Secondary: Active TB rates six months after IPT completion.

b) **Explore the mechanisms that may drive the economic incentives to increase virologic suppression.**
Potential mediators will be reductions in alcohol use and level of IPT adherence.

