In Aim 3, we hypothesize that the proposed alcohol (Aim 1) and IPT adherence (Aim 2) interventions will improve ART adherence, leading to increased viral suppression that persists after incentives are withdrawn. Our Aim 3 hypothesis is supported by two observations. First, [name] et al. have demonstrated that reductions in alcohol or drug use targeted by incentive interventions can lead to improvements in other health behaviors, including reductions in HIV-risk behavior, cigarette smoking, other drug use, psychiatric symptoms and hospitalizations.^{55,85-87} Second, there is evidence that short-term incentives can result in behavior changes that persist after incentives are removed, due to the formation of healthy habits.^{41,88-90} However, some studies report diminishing impact after withdrawal of incentives,^{2,57} and it has been suggested that incentives displace intrinsic motivation, with no long-term positive impact on behavior.⁹¹ Given this mixed evidence, we will examine whether incentives to reduce alcohol use and improve IPT adherence result in improvements in ART adherence that persist after incentives are withdrawn, as measured by HIV virologic suppression six months post-intervention. As there is no measure of IPT efficacy other than lack of progression to active TB, we will also monitor for active TB by trial arm during and after IPT in this high-risk, HIV/TB co-infected population.

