5.4. Intervention

5.4.1. Aim 1: Alcohol reduction intervention

We will compare an economic incentive-based intervention, to no incentives, in order to promote reductions in heavy alcohol use over six months of IPT in HIV/TB co-infected adults. In the Aim 1 intervention arms, participants will be told at baseline and at each study visit that each time they come to a monthly IPT refill visit and have a negative urine EtG test (detects alcohol consumption), they will instantly win a prize by drawing a lottery scratch card. Prize types and probabilities of winning a low, medium, or high-valued prize are described in section 5.4.3. The number of lottery scratch cards awarded per participant will increase by one card at each subsequent visit with a negative urine EtG results, thereby providing an escalating prize incentive (best practice for incentive-based interventions^{2,147,148}) for sustained reductions in alcohol use (see Figure 2).

If a participant has a positive urine EtG test, no lottery scratch cards will be given for alcohol use reduction, and the participant will “reset” to drawing one lottery card if the urine is EtG negative at the subsequent visit. Escalating incentives with a “reset” were chosen to offer greater reward for continuous, rather than intermittent, reductions in alcohol use over the full six months of IPT, so as to minimize risk of hepatotoxicity on INH.²⁷ INH refill visits will be scheduled at the beginning of the week whenever possible, as our previous data show that the majority of heavy drinkers use alcohol during weekend days.

Figure 2. Example of escalating prize incentive for participant enrolled in

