5.4.4. Aim 3: Impact assessment of intervention

At month 12 (6 months after the Aims 1 and 2 trial completion), we will perform a study interview with participants regarding their health and alcohol use, measure PEth levels and plasma HIV viral load, and conduct TB case-finding through symptom screening, with follow-up chest x-ray and/or sputum MTB/RIF Xpert assay for symptomatic persons (Table 2).

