Missed or late visits: If a participant misses a scheduled visit, the visit will be rescheduled within the coming 4 weeks after the missed visit, and missed visits (i.e. no-show for a clinic appointment >3 days after the scheduled clinic appointment date) will automatically prompt an incentive “reset” to baseline (i.e. drawing one card only if the incentive condition is met). Late or early visits, defined as coming to an appointment more than 3 days of an assigned appointment date, will result in an incentive “reset” to baseline. On rare occasion, exceptions to the protocol for early, late, and missed visits may be considered at the discretion of the study coordinator and study PIs. All participants will be allowed up to 9 months from INH initiation to complete a 6-month course (180 tablets) of INH, taking missed visits/refills into account. Participants that miss ≥3 months of visit time will be considered as having failed to complete IPT.

Figure 3. Study visit flow chart: Aims 1, 2 & 3.

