Hepatotoxicity. A secondary outcome will be treatment discontinuation due to a Grade 3/4 hepatotoxicity at any time during the treatment period. Grade 3/4 hepatotoxicity is defined as in previous trials³ as ALT or ALT $>3-5$ ULN and symptoms (nausea, vomiting, jaundice, or fatigue) or ALT or AST >5 ULN, regardless of symptoms. Study clinicians, blinded to intervention arm, will determine treatment discontinuation.

HIV viral suppression. The primary outcome for Aim 3 will be HIV viral suppression 12 months post-enrollment. We will also examine viral load six months post-enrollment as a secondary outcome for Aim 3.

Active TB. A secondary outcome for Aim 3 will be active TB at any time during the 12 months post-enrollment. Active TB will be defined as confirmed (if Xpert MTB/RIF assay positive) or suspected (based on chest x-ray findings or response to anti-TB treatment in symptomatic, Xpert assay negative persons).

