Figure 1. Schematic of study design and aims of the Drinkers' Intervention to Prevent TB (DIPT) trial

Objectives

The DIPT trial is designed to achieve three aims. Aim 1: To determine the effectiveness of financial incentives contingent on low alcohol use (Arms 2 and 4) versus no alcohol incentives (Arms 1 and 3) to reduce heavy drinking during INH preventive therapy. The hypothesis for Aim 1 is that participants receiving incentives for negative urine EtG testing will have lower alcohol use, determined via a medium-term alcohol biomarker during INH, compared to participants receiving no alcohol incentives. Aim 2: To determine the effectiveness of financial incentives contingent on high INH adherence (Arms 3 and 4) versus no INH adherence incentives (Arms 1 and 2) to increase INH adherence during INH preventive therapy. The hypothesis for Aim 2 is that participants receiving incentives for positive POC IsoScreen testing will have better adherence to INH, determined via objective monitoring, than participants receiving no INH adherence incentives. Aim 3: To determine the effectiveness of financial incentives (Arms 2, 3, and 4) versus no financial incentives (Arm 1) on HIV virological suppression after completing their INH preventive therapy. The hypothesis for Aim 3 is that participants receiving financial incentives have higher rates of HIV virological suppression six months after INH completion.

Primary outcomes

The study has two primary outcomes. The primary outcome for Aim 1 (i.e., to estimate the effect of incentives contingent on negative urine EtG tests) is no heavy alcohol consumption over the six months of INH preventive therapy, a binary variable. This is defined as a composite outcome of both PEth <35 ng/mL and negative AUDIT-C score at both the 3- and 6-month visits. We will use standard AUDIT-C cutoffs (≥ 3 for women and ≥ 4 for men) to define heavy drinking.

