The primary outcome for Aim 2 (i.e., to estimate the effect of incentives contingent on a positive IsoScreen test) will be INH adherence measured as >90% pill-taking days by MEMS cap opening during the six-month course of INH or the time prescribed for those who were instructed to discontinue INH, a binary variable. The participants were given up to 9 months to complete a 6-month (180-pill) INH preventive therapy course. Therefore, MEMS adherence is defined as the number of pill bottle openings (no more than 1 per day counted) within a 270-day window divided by the number of prescribed doses (180, unless the participant discontinued the medication).

The outcome for Aim 3 is treated as a secondary outcome (see below).

Secondary outcomes

The secondary outcome for Aim 1 is PEth as a continuous variable measured at the 6-month visit.

The secondary outcome for Aim 2 is MEMS-measured adherence as a continuous variable (defined as the proportion of days with a bottle opening out of number of days prescribed within 9 months of randomization).

The outcome of Aim 3 is HIV virological suppression defined as an undetectable plasma HIV viral load at the 12-month visit (a binary variable). Another secondary outcome for Aim 3 will be HIV virological suppression at the 6-month visit (a binary variable).

Another secondary outcome is INH preventive therapy discontinuation due to grade 3 or grade 4 hepatotoxicity at any time while receiving INH (a binary outcome). Grade 3 hepatotoxicity was defined as AST or ALT ≥ 5 ULN or based on symptoms that met pre-specified Grade 3 criteria for hepatotoxicity. Grade 4 hepatotoxicity was defined as AST or ALT ≥ 10 ULN or based on symptoms that met pre-specified Grade 4 criteria for hepatotoxicity.

Finally, active TB during the 12 months of follow-up (a binary outcome) is also a secondary outcome. Active TB is defined as confirmed (if Xpert MTB/RIF assay positive) or suspected (based on chest x-ray findings or response to anti-TB treatment in a symptomatic and Xpert assay negative person).

Descriptive statistics

We will report the distribution of baseline covariates overall and by randomization arm. For continuous variables, we will provide the median, mean, standard deviation, 0th, 25th, 50th, 75th, and 100th percentiles. For categorical variables, we will provide frequencies and proportions. Differences between arms will not be evaluated based on statistical significance.

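### Aim 3 claims viral suppression six months after INH completion, but the viral load is fixed at month 12 and INH may run to month 9, so the interval can be as short as about three months

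*SAP*

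**What the plan says.** **The aim is anchored to the end of INH.** The SAP (Objectives, Aim 3) expects that "participants receiving financial incentives have higher rates of HIV virological suppression six months after INH completion". Protocol section 2.1 gives the Aim 3 primary outcome as "The proportion with undetectable HIV viral load six months post-IPT completion". Protocol section 3 adds the purpose: to learn whether gains in ART adherence are ones "that persist after incentives are withdrawn, as measured by HIV virologic suppression six months post-intervention".

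**The outcome is anchored to enrolment.** Protocol section 5.7.1 states: "The primary outcome for Aim 3 will be HIV viral suppression 12 months post-enrollment". The SAP (Secondary outcomes) has "HIV virological suppression defined as an undetectable plasma HIV viral load at the 12-month visit". Protocol section 5.4.4 treats the two anchors as the same, describing month 12 as six months past the end of the Aims 1 and 2 trial.

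**INH may end later than month 6.** Protocol section 5.5 says "All participants will be allowed up to 9 months from INH initiation to complete a 6-month course (180 tablets) of INH". The SAP repeats the nine-month allowance and counts MEMS openings over 270 days. Protocol section 6.2 continues pregnancy questions through months 7 to 9 for women who have not finished by month 6.

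**INH was interrupted in 2020.** The SAP (Impact of COVID-related disruptions) reports that activities were paused on 19 March 2020, that participants on INH were told to stop, and that study visits resumed on 26 May 2020.

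**The concern.** Aim 3 asks about durability, and Protocol section 3 acknowledges mixed evidence on whether incentive effects last. The length of the interval is therefore part of the claim. If some participants finish INH in month 7, 8 or 9 and still have their viral load at month 12, the result covers a mixture of intervals and cannot properly be reported as suppression six months after INH ended.

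The SAP widened the Aim 2 adherence window to allow for late completion but left the Aim 3 hypothesis as it was. Neither document moves the month-12 visit for late completers, and neither plans to describe the time actually elapsed. The SAP is dated August 2022, so the 2020 interruption was already known when the hypothesis was written.

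**Working it through.** **Inputs**
- Viral load: month 12 from enrolment (Protocol 5.7.1; SAP Secondary outcomes).
- Nominal INH course: 6 months, 180 doses. Permitted maximum: 9 months, 270 days (Protocol 5.5; SAP Primary outcomes).
- Lockdown: 19 March to 26 May 2020 (SAP, COVID paragraph).
- Aim 3 power: 680 enrolled, 1:1:1:1 allocation, 15% loss, 67% v 84%, alpha 0.0167 per comparison, continuity correction (Protocol 5.3, 5.9.1 and 5.9.3).

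**The plan's own interval.** Interval = month of viral load − month of INH completion. On time: 12 − 6 = 6 months (365 − 180 = 185 days). The stated six months reproduces, but only for on-time completers.

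**Interval over the permitted range**

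| INH completed at month | Interval to month-12 viral load |
|---|---|
| 6 | 6 months |
| 7 | 5 months |
| 8 | 4 months |
| 9 | 3 months (365 − 270 = 95 days) |

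A viral load six months after a month-9 completion would fall at month 15 (270 + 180 = day 450). No visit is scheduled then. The Protocol starts the nine-month clock at INH initiation and the SAP at randomisation. If INH began some days after enrolment, the minimum is slightly under three months.

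**Lockdown illustration.** 12 + 30 + 26 = 68 days, about 2.2 months. Completion: 6 + 2.2 = 8.2 months. Interval: 12 − 8.2 = 3.8 months. This assumes that the participant resumed INH on 26 May 2020 and missed nothing else, and that the month-12 visit was not moved. The SAP confirms none of these.

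**Aim 3 power, to see whether timing enters it.** Evaluable: 680 × 0.85 = 578, or 578 / 4 = 144.5 per arm. The uncorrected requirement for 67% v 84% at 80% power is m = 133 per arm. With continuity correction, n = (m/4) × [1 + √(1 + 4/(m × 0.17))]² = (133/4) × [1 + √1.177]² ≈ 144.5, rounded up to 145. Power at 144.5 per arm is 80.1%, matching the stated 80%. No timing input appears, so the figure is unaffected.

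**The case against.** The best defence is that the operational definitions are clear. Both documents fix the viral load at month 12, so nobody can be in doubt about which measurement is analysed. A fixed clock from enrolment is sound practice in a randomised trial, and the six-month wording can be read as describing the nominal schedule. The SAP also treats Aim 3 as secondary, and three months is a worst case: participants taken off INH early for toxicity or pregnancy have intervals longer than six months. All of this stands, and it is why the month-12 comparison needs no change. It does not rescue the hypothesis sentence, which names INH completion as the anchor without qualification. The SAP's COVID analyses do not cover the point either. They compare baseline characteristics and explore effect modification, but do not look at time to the viral load.

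Several stronger readings are tempting, and the documents do not support them.

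- *The gap after incentives were withdrawn was also shortened.* Prizes are tied to refill visits (participants qualify "each time they come to a monthly IPT refill visit and have a negative urine EtG test"), so they could have followed late refills. But Protocol section 5.5 schedules refill visits only to month 6, and Table 2 shows urine tests only to month 6. If prizes ended there, the six-month post-incentive interval holds as written. The documents do not settle it.
- *If prizes ended at month 6, Aim 2 is broken because days 181 to 270 carry no incentive.* Aim 2 estimates the effect of assignment on adherence. Nothing in it requires an incentive on every day of the window.
- *The reset rule makes the interval differ by arm.* The reset changes how many cards are drawn, not when INH ends. A difference by arm is possible, because incentives might change how quickly the course is finished, but neither its existence nor its direction can be read from the plan. An overstatement of persistence therefore cannot be asserted.

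**Conclusion.** The concern holds for the interval after INH completion. The six months in the hypothesis is correct for on-time completers and falls to about three months (about 95 days) at the limit the plan itself allows. Participants stopped in the lockdown are likely to lie in between, at about 3.8 months under the assumptions shown. How much this matters depends on the proportion finishing in months 7 to 9, which the documents do not give.

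The affected items are the label and any conclusion of six-month persistence after INH completion. The intent-to-treat comparison at month 12 remains valid and the Aim 3 power stands. Whether the interval since the last prize is also short is open, since it depends on when prize visits ended.

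**What to change.** 1. In the SAP Objectives and the Aim 3 outcome text, state the hypothesis and the eventual conclusion as suppression 12 months after randomisation, nominally six months after the scheduled end of INH. Remove the unqualified reference to INH completion, and read the matching line in Protocol section 2.1 the same way.
2. Tabulate by arm the time from last INH dose or visit to the month-12 viral load and, for Arms 2 to 4, the time from the last prize-eligible visit.
3. Reconcile Protocol sections 5.4.1 and 5.4.2, which tie prizes to refill or clinic visits, with section 5.5 and Table 2, which end those visits and tests at month 6, so that readers know when prize visits ended.
4. Keep the intent-to-treat month-12 analysis as the only inferential one. Do not add a subset limited to viral loads taken some minimum time (say 150 days) after the last prize or INH visit. That would select on a post-randomisation variable which incentives may influence, use different anchors in Arm 1 and Arms 2 to 4, and rest on a cut-off with no source in the documents.

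The cost is a few lines of SAP text and one descriptive table from visit and MEMS dates, with no new data collection. The price is a more modest claim for Aim 3.

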5.7. Measurements

5.7.1. Outcome variables

Reducing heavy alcohol consumption: The main goal of the Aim 1 intervention is to reduce the level of drinking to a level most likely to decrease the risk of INH toxicity. Thus we have chosen no/non-heavy alcohol consumption as the Aim 1 primary outcome. While we are incentivizing negative urine EtG tests at INH refill visits as our *intervention*, our *trial outcome variable* captures reducing drinking over the six-month duration. We will consider PEth <35 ng/mL and AUDIT-C negative (modified to refer to the prior 3 months) at 3 and 6 months as refraining from heavy drinking during the entire period of risk. The AUDIT-C will be used because it is comprised of ranges for typical numbers of drinks and frequency of heavy drinking, rather than precise number of drinks consumed (as in the Timeline Follow Back), which can be difficult to quantify for the traditional and home-brewed beverages frequently consumed in rural African settings.^{99,157} We have adapted the AUDIT-C to cover the prior 3 months (as opposed to the past year) as a measure of current drinking, and use standard cutoffs (≥ 3 for women and ≥ 4 for men) to represent heavy drinking. We will use 35 ng/mL as the PEth cutoff as described above (see Preliminary Studies). We will examine other measures of heavy drinking in sensitivity analyses, including number of drinking days in the prior 30, number of heavy drinking days (defined as ≥ 4 or ≥ 5 drinks/occasion by women and men), and PEth as a continuous variable.

IPT adherence. As above, we are incentivizing positive IsoScreen tests at INH refill visits, but our second trial *outcome variable* is IPT adherence over the entire six months. While there is no gold standard for determining medication adherence, MEMS adherence has been highly predictive of undetectable HIV viral load,^{83,158,159} is considered the reference standard,^{72,83,160,161} and therefore will be our primary measure of adherence. MEMS adherence will be defined as the number of pill bottle openings (no more than 1 per day counted) divided by the number of prescribed doses (180, unless taken off the medication early). The primary outcome for Aim 2 will be the proportion of participants that achieve >90% MEMS adherence to INH during prescribed IPT. We will examine other measures of INH adherence in secondary analyses, including drug concentration (ng/mg) in hair samples at 3 and 6 months, and continuous MEMS adherence.

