An exploratory outcome for Aim 2 will be drug concentration (ng/mg) in a subset of small hair samples. Hair levels of INH measure long-term and cumulative exposure to INH will be used to determine if short-term increases in adherence translate to sustained changes in behavior.

Intervention-by-time-interaction. For Aims 1 and 2, we will check for the presence of intervention-by-time interaction by conducting separate analyses at months 3 and 6. We will use generalized estimating equations with an independent working correlation matrix for binary outcomes and random effect models for continuous outcomes.

Impact of COVID-related disruptions. Recruitment started on April 16 2018 and study activities were paused in March 19, 2020 due to a lockdown enforced by the Ugandan government in response to the COVID-19 pandemic. During this time, all research activities were stopped and participants on INH were contacted and instructed to stop taking their INH pills immediately, as there were no means to effectively monitor for liver toxicity. Study visits resumed on May 26, 2020 and enrollment resumed on June 16, 2020. We will conduct several descriptive statistics to examine to what extent the lockdown and the pandemic might have impacted the generalizability of the trial's findings. First, we will group the participants based on whether their scheduled INH completion date was before versus on or after March 19 2020 and will compare their baseline characteristics including measures of drinking. Second, we will perform an analysis to explore whether completion of INH before or after pandemic interruption acts as potential effect modifier of the incentive interventions.

Subgroup analyses. We will perform analyses to explore potential effect modifiers of the incentive interventions. For Aims 1 and 2, the potential moderators of interest are: sex, baseline level of alcohol use, time and risk preferences, and readiness to change . For each aim, we will fit separate models including 2-way interactions between randomization group and each potential effect moderator, as well as a model testing the interaction between the two

interventions. If an interaction is significant, subsequent stratified analyses will be conducted to explore the effect of the economic incentive interventions by categories of the moderator.

References

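### The SAP's Aim 2 adherence formula shortens the dose denominator when INH is discontinued but keeps counting bottle openings to day 270, contrary to the outcome definition beside it

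*SAP*

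**What the plan says.** The SAP (Primary outcomes, Aim 2) deals with the outcome in three steps.

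- The lead sentence sets the measure, "INH adherence measured as >90% pill-taking days by MEMS cap opening", and its period: "during the six-month course of INH or the time prescribed for those who were instructed to discontinue INH".
- It then explains why a longer window is needed: "The participants were given up to 9 months to complete a 6-month (180-pill) INH preventive therapy course".
- It then gives the operational formula: the "number of pill bottle openings (no more than 1 per day counted) within a 270-day window divided by the number of prescribed doses". The denominator is the "number of prescribed doses (180, unless the participant discontinued the medication").

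Protocol section 5.7.1 uses the same denominator, with a reduction for early stopping, but has no 270-day window in its formula. It defines success as the proportion who "achieve >90% MEMS adherence to INH during prescribed IPT".

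The SAP's section on COVID-related disruptions (Exploratory analyses) records that at the March 2020 pause "participants on INH were contacted and instructed to stop taking their INH pills immediately". Visits resumed on 26 May 2020. Neither document says how a stop followed by a restart enters the adherence formula.

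**The concern.** In the formula, discontinuation changes only the denominator. Nothing ends the count of openings at the stop, drops later openings or limits the ratio to 100%. An opening on a day when the participant had been told not to take INH therefore adds to the numerator with no prescribed dose to match it. That is not adherence, yet it can carry a participant over the 90% line.

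The lead sentence points the other way, so two programmers, each able to cite the SAP, could score the same participant differently on a primary endpoint. Under the literal reading the error has one direction: it can turn failures into successes but never the reverse. The planned control group has more failures to convert, so it also tends to narrow the difference between the groups.

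**Working it through.** **Plan's own figure.** Protocol sections 5.9.1 and 5.9.2 give 680 enrolled, 10% loss, a two-sided 5% test, a continuity-corrected chi-square, and 62% v 50% at 80% power.

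- Evaluable: 680 × 0.9 = 612, or 306 per side of the factorial comparison.
- Power = Φ{[d − 1/n − 1.96·√(2p̄(1−p̄)/n)] / √([p₁(1−p₁) + p₂(1−p₂)]/n)}, where n = 306, d is the difference and p̄ the mean of the two proportions.
- At 62% v 50%, power is 83.0%. The difference detectable at 80% power is about 11.6 points, which rounds to the stated 12. The plan's figure is sound and slightly conservative.

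**One participant, scored two ways.** Success means more than 90%. With D prescribed doses, the smallest passing count is floor(0.9·D) + 1. For a stop at day 60, D = 60 and 55 openings are needed (54/60 is exactly 90% and fails).

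| Openings before stop | Openings after stop | Count ended at stop | Formula read literally |
|---|---|---|---|
| 52 | 3 | 52/60 = 86.7%, failure | 55/60 = 91.7%, success |
| 45 | 10 | 45/60 = 75.0%, failure | 55/60 = 91.7%, success |

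After a day-60 stop, 270 − 60 = 210 days of the window remain in which such openings could be recorded.

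**Effect on the comparison.** Let s be the share who stop early and f the share of failures among stoppers who flip. Assume that both are equal across arms and that stoppers have the same true success rate p as everyone else. The scored rate is then p + s·f·(1 − p). The documents give no value for f; 0.5 is an assumption. For s, 4% is the top of the 0.1–4.0% Grade 3/4 hepatotoxicity range in protocol section 3, and 10% is illustrative.

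| s | Control | Intervention | Difference | Power |
|---|---|---|---|---|
| 0 | 50% | 62% | 12.0 points | 83% |
| 4% | 50 + 4 × 0.5 × 0.50 = 51.0% | 62 + 4 × 0.5 × 0.38 = 62.76% | 11.8 points | 82% |
| 10% | 50 + 10 × 0.5 × 0.50 = 52.5% | 62 + 10 × 0.5 × 0.38 = 63.9% | 11.4 points | 79% |

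At 4%, the overall success rate rises by (1.0 + 0.76)/2 = 0.88 points, about 5 of 612 participants. At the 0.1% end of the range (680 × 0.001 = 0.7 participants) the effect is negligible.

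If instead the same number of participants flip on each side, the difference does not move and power is almost unchanged: 83.1% to 84.3% for s of 4% or 10% with 10% to 50% of all stoppers flipping.

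**Pause and restart.** Take a participant paused at day 100 with 60 openings, who records 40 more after a restart. If the denominator stays at 180, the score is 100/180 = 55.6%. If the participant is coded as discontinued and the count ends at the pause, it is 60/100 = 60%. Only a mixture, with the denominator frozen at the pause and later openings still counted, gives 100/100 = 100%.

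**The case against.** The strongest reply is that the outcome is already confined to prescribed time, by the SAP's lead sentence ("or the time prescribed for those who were instructed to discontinue INH") and by protocol section 5.7.1. On this view the 270-day window only lets late completers finish 180 pills, and a careful programmer would read the formula in that light. This is a fair account of the intent. It does not settle the matter, because the formula is the sentence that gets coded, and it does not carry the restriction.

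Second, the route is narrow in practice. Protocol section 6.2 provides for home retrieval of dispensed medication when hepatotoxicity is found after the visit, and IsoScreen incentives end once INH is discontinued for toxicity or pregnancy. Both points stand and limit the size. Retrieval is not described for pregnancy stops or for the lockdown, however, and ending an incentive does not stop a cap from recording.

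Two stronger readings are tempting and should be resisted:

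- A reader might infer that the lockdown badly inflated the endpoint and cost much of the power. That needs the mixed coding shown above, which neither document describes, and a figure for the share on INH at the pause, which neither document gives. A participant who resumes the 180-dose course could equally keep a denominator of 180.
- A reader might infer that the continuous adherence outcome can exceed 100%. The SAP words that outcome separately, as a proportion of the days prescribed, and this naturally counts prescribed days only.

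**Conclusion.** The point holds as an internal conflict in the definition of a primary endpoint. Applied as written, the formula mis-scores some participants who were told to stop INH, always towards success.

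The likely effect is small. For toxicity stops alone it moves the overall success rate by less than about one point. The planned difference falls from 12 to about 11.8 points with 4% stopping, and to about 11.4 points, with power of about 79%, at 10%. These sizes rest on half of the failures among stoppers flipping, with equal stopping and flipping probabilities in both groups; the documents supply neither. Nothing in them shows unequal flipping between arms, so no differential bias is claimed. Any lockdown effect cannot be sized until the coding of paused participants is known. That the SAP, dated August 2022 and describing the pause, gives no such rule is part of the point.

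It is worth correcting because the endpoint is primary and the correction costs almost nothing, not because the trial's conclusion is likely to turn on it.

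**What to change.** Amend the formula in the SAP's Aim 2 primary outcome as follows.

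- For participants instructed to discontinue INH, end the opening count at the instructed stop date, the same date that ends the denominator.
- For a pause followed by a restart, exclude openings during the pause, and count both openings and prescribed doses after the restart.
- For everyone else, keep 180 doses against the 270-day window. A general rule that numerator and denominator must span the same days would remove the deliberate allowance for late completers.
- Confirm that the continuous MEMS outcome counts openings on prescribed days only.

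This changes scoring only and leaves the rules for stopping or restarting INH alone. It costs one sentence and a date filter on the MEMS records, using the stop and restart dates. The scored adherence proportion may fall slightly.
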